4.1 Full Analysis Set

The full analysis set (FAS) will consist of all subjects who are enrolled and receive at least one dose of study drug. This will be the primary analysis set for efficacy analyses.

4.2 Modified Full Analysis Set

The modified FAS (mFAS) will consist of the subset of the FAS subjects who have either probable or proven IA or IM diagnosis at baseline or up to 10 days after first dose. Subjects with a possible diagnosis of IA or IM will not be included in this subset. The mFAS will be a secondary analysis set for efficacy analyses. Select demographic and baseline characteristics may also be summarized for the mFAS.

4.3 Safety Analysis Set

The safety analysis set (SAF) will consist of all subjects who are enrolled and receive at least 1 dose of study drug. For this study, the SAF is the same as the FAS. For the statistical summary of the safety data, the SAF will be used.

4.4 Pharmacokinetics Analysis Set

The pharmacokinetic analysis set (PKAS) consists of all subjects who took at least 1 dose of study drug and who have at least 1 plasma concentration. Inclusion of subjects in the PKAS with missing data or major protocol deviations will be considered by the pharmacokineticist on a case-by-case basis.

The PKAS will be used for all summaries and analyses of the pharmacokinetic data.

5 ENDPOINTS

5.1 Safety Endpoints

Safety endpoints will include adverse events (AEs), vital signs, electrocardiogram (ECGs) and laboratory parameters.

5.2 Efficacy Endpoints

5.2.1 Primary Efficacy Endpoint

The primary efficacy endpoint will be all-cause mortality through day 42. Any death that occurred after first dose of study through day 42 will be included. Any lost to follow-up between first dose and day 42 will be considered a death.

5.2.2 Secondary Efficacy Endpoint(s)

5.2.2.1 Key Secondary Endpoint(s)

The key secondary efficacy endpoints will be all-cause mortality through day 84 and EOT. Any death that occurred after first dose of study drug through day 84 and EOT will be included. Any lost to follow-up between first dose and day 84 and EOT will be considered a death.

5.2.2.2 Additional Secondary Endpoints

Additional secondary efficacy endpoints will include:

- Adjudication Committee (AC) and Investigator assessment of clinical, radiological and mycological response through day 42, day 84 and EOT.
- AC assessment of overall response at day 42, day 84 and EOT

5.3 Other Endpoints

Other endpoints encompass pharmacokinetic variables, including plasma trough (pre-dose) levels on days 7, 14, 21, 42 and 84 or EOT.

6 STATISTICAL METHODOLOGY

6.1 General Considerations

Continuous data will be summarized descriptively including the number of subjects (n), mean, standard deviation (SD), median, minimum and maximum. Categorical data will be summarized by frequencies and percentages with 95% confidence interval (CI). Efficacy data will be summarized by type of infection including IA, IM and mixed IA/IM infected subjects. Safety summaries will also be presented for by type of infection. The IA group will comprise subjects with IA infection without known IM infection; the IM group will comprise subjects with IM without known IA infection; and the IA/IM group will comprise subjects with mixed IA/IM infection. Analysis Windows will be used and, for those parameters with weekly data collection, are illustrated below in Section 6.9. For those parameters collected less often appropriate windows will be defined. Note that, IM and IA/IM infected subjects will be reported to conclusion of treatment and 60 day follow-up although day 180 is not considered an endpoint analysis. Kaplan Meier (K-M) analyses for mortality will incorporate all survival data to day 240 if IM subjects are included.

All data summarization and analyses will be performed using SAS® Version 9.1.3 or higher. Specifications for table, figures and data listing formats can be found in the Tables, Listings, and Figures (TLF) specifications.

6.2 Study Population

In general, data such as subject disposition, demographics and baseline characteristics will be summarized for FAS population.

6.2.1 Disposition of Subjects

Disposition of subjects will be summarized for all subject.

Number of subjects who complete or prematurely discontinue from treatment or study (i.e., follow up period) will be summarized. For each discontinuation, the primary reason reported by the investigator will be summarized. Number and percentage of subjects for each analysis population will be summarized.

6.2.2 Protocol Deviations

The number and percentage of subjects with the following protocol deviation (PD) criteria will be summarized for each criterion. Subjects deviating from a criterion more than once will be counted once for the corresponding criterion.

Some unique identifiers will be as follows:

- PD1 - Entered into the study even though they did not satisfy entry criteria,
- PD2 - Developed withdrawal criteria during the study and was not withdrawn,
- PD3 - Received wrong treatment or incorrect dose,
- PD4 - Received excluded concomitant treatment.

6.2.3 Demographic and Other Baseline Characteristics

Demographic and other baseline characteristics will be summarized descriptively for FAS and mFAS. Descriptive statistics for age, weight, body mass index (BMI) and height at study entry will be presented. Frequency tabulations for sex, ethnicity, age cohorts and race will be presented.

Please note that all Physical Examination Data will be reported in listing. For Post-Baseline visits, recorded abnormal findings/conditions that have worsened from Screening/Baseline, and are clinically significant, will be recorded on the Adverse Events form.

6.2.4 Underlying Diseases or Conditions

All primary underlying diseases and risk factors will be reported using the FAS and mFAS populations. Primary underlying disease diagnosis will be listed with full status of disease diagnosis, timing, severity and/or resolution level. This data will be tabled using Medical Dictionary for Regulatory Activities (MedDRA) codes and listed alphabetically. The number and percentage of subjects will be summarized by diagnosis [system organ class/preferred

term (PT)] and presentation status (New Diagnosis, Remission and Relapse). The summary will also include solid organ transplant and bone marrow or other progenitor cell transplant by type.

6.2.5 Baseline IFI

The descriptive summary includes subjects in each category of fungal infection site and fungal culture organism(s) by genus at baseline using the FAS and mFAS populations. Baseline will include all data collected from Day -28 to Day 10, as relevant. These include Host factors, Clinical factors, Mycological Criterion and Other invasive fungal disease (IFD) signs.

In addition, categorization of patient's fungal infection will include Proven, Probable or Possible. This categorization is evaluated again on Day 10. Day 10 may provide more information than baseline given time for additional confirmatory laboratory results for subjects that may upgrade or downgrade fungal diagnosis. For example, a final baseline evaluation of subject status Proven, Probable or Possible will be determined using the combination of data collected.

6.2.6 Previous and Concomitant Medications

Prior, concomitant and post medications will be summarized by therapeutic subgroup (Anatomical Therapeutic Chemical [ATC] 2nd level) and chemical subgroup (ATC 4th level) and preferred World Health Organization (WHO) using the FAS and mFAS populations. Subjects taking the same medication multiple times will be counted once per medication and investigational period. A medication which can be classified into several chemical and/or therapeutic subgroups is presented in all chemical and therapeutic subgroups. Systemic antifungal therapies will be reported separately.

Previous medications are defined as medications that subjects started and ended prior to first administration of study medication. Analysis Windows will be used, See below Section 6.9. Concomitant medications are defined as any medications that subjects took after the first dose of study medication and through 60 days post EOT. Medications that started prior to first administration of study drug and continued while study drug was given will be counted in both previous and concomitant medications.

6.2.7 Infectious Disease History

History of all fungal, viral and bacterial infections within 14 days prior to screening will be reported among FAS and mFAS. The data will be coded using MedDRA. The number and percent of subjects in each PT will be presented in alphabetic order. All medical history will be included in the listings.

6.3 Study Drug Exposure and Compliance

Study drug exposure will be descriptively summarized for the SAF and mFAS population. Extent of exposure is defined as the number of days between the start and the end date of study drug, where the duration will be calculated by: (end date – start date+1). Additionally

average daily mg dose and average daily mg/kg doses, for LD and maintenance, IV and Oral summaries will be presented using descriptive statistics for continuous data.

The number and percent of subjects with an extent of exposure will be summarized within the following day ranges: >0 to ≤ 2 days, >2 to ≤ 7 days, >7 to ≤ 14 days, >14 to ≤ 21 days, >21 to ≤ 42 days, >42 to ≤ 56 days, >56 to ≤ 84 days, and >84 days. In addition, cumulative exposure will be summarized by the number and percent of subjects for the following categories: ≥ 1 day, ≥ 7 days, ≥ 14 days, ≥ 21 days, ≥ 28 days, ≥ 42 days, ≥ 56 days and ≥ 84 days.

6.4 Analysis of Efficacy

Efficacy variables will be summarized for IA, IM and IA/IM disease groups using FAS and mFAS populations. No formal inferential analyses will be performed. Frequencies, percentages, min/max and 95% CIs will be part of the description/summary of the data.

6.4.1.1 Analysis for Primary Efficacy Endpoint(s)

The primary efficacy endpoint will be all-cause mortality through day 42. Any death that occurred after first dose of study drug through day 42 will be included where each subject will be either classified as a dead or alive. Subjects who died on or before day 42, as well as subjects who are lost to follow-up before day 42 will be counted as deaths. The crude all-cause mortality rate will be calculated by dividing the number of deaths by the number of FAS subjects, and a 2-sided exact 95% CI will be calculated.

6.4.1.2 Other Analysis of Primary Efficacy Endpoint(s)

All-cause mortality rate over time will be estimated using Kaplan-Meier method. This analysis will generate a survival function from Day 1 through Day 42. A subject without reported death will be censored on the patient's last assessment day. The cumulative probabilities of mortality rates (100%-survival rates) by Day 42 will be presented.

6.4.1.3 Sensitivity Analysis for Primary Efficacy Endpoint

The primary efficacy endpoint will be analyzed as in Section 6.4.1.1 using the mFAS population. In addition mFAS patients taking excluded concomitant medications used to treat IFDs will be eliminated for analysis of primary endpoint.

A secondary sensitivity analysis will apply a condition on the crude success rate of overall outcome of treatment evaluated by the AC on Day 42. Patients who die before or on Day 42 will be considered failures even if the DRC considers them successes. The crude success rate of overall outcome of treatment evaluated by the AC at Day 42 incorporating this condition will be summarized. A 95% CI for this crude success rate of overall outcome of treatment evaluated by the AC at Day 42 will be calculated using exact confidence limits. This sensitivity analysis will only be performed if any patient died by Day 42 is considered a success for treatment by the AC.

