5.1.2 Previous and Concomitant Treatment (Medication and Nonmedication Therapy)

Systemic antifungal medications taken for IM or IA or suspected mycoses and other medication taken within 28 days prior to the screening visit and up to the first dose of study

drug (investigational period) will be documented as prior antimycotic medications or other prior medication, respectively.

Medications taken after the first dose of study drug and up to EOS will be documented as concomitant medications.

Prior and concomitant medications and nonmedications to be documented include, but are not limited to, the following: vitamins, herbal remedies (e.g., St. John's Wort, valerian) and over-the-counter and prescription medications. Any medications taken for treatment of pain symptoms will be documented as such.

Subjects are instructed not to take any concomitant medication without first consulting the investigator or study coordinator throughout the duration of the study.

Prohibited Therapies:

Treatments with concomitant drugs that are strong inhibitors or inducers of CYP3A4 are prohibited, including ketoconazole, high dose ritonavir, rifampin/rifampicin, carbamazepine and St. John's Wort or long acting barbiturates (e.g., phenytoin). Concomitant use of sirolimus, atorvastatin, cyclosporine, tacrolimus, midazolam, bupropion, mycophenolate mofetil and digoxin should be made with caution.

Treatments with concurrent drugs that are CYP3A4 substrates and have a narrow therapeutic range (e.g., vincristine) should be used with caution, and if clinically warranted, consider reduction of substrate dose.

Use of other systemic antifungals is prohibited during study drug administration.

Subjects taking prohibited medications who are willing to discontinue these medications, as clinically indicated and based upon the investigator's recommendation, may washout over a period of 5 half-lives on a schedule determined by the investigator.

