6.4.3.4 AC-assessed Clinical Response

Clinical response will be defined as follows:

| Summary | Category | Outcome |
|---------|----------|--|
| Success | Complete | 
 Resolution of all attributable clinical symptoms and physical findings |

| | | |
|---------------|---|--|
| | Partial | 
 Resolution of at Least some of the clinical symptoms and physical findings associated with IFD |
| Failure | Stable | 
 Minor or no change in clinical symptoms and physical findings associated with IFD |
| | Progression | Worsening or new clinical symptoms and physical findings associated with IFD, or if alternative systemic antifungal treatment is required |
| Not Evaluable | Not Assessed | |
| | No clinical signs or symptoms at baseline | |

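### SAP 6.4.1.3 deletes mFAS patients who took excluded antifungals; the resulting Day 42 death rate describes a selected subset, can err in either direction, and is not a sensitivity analysis

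*SAP*

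**What the plan says.** The primary analysis (SAP 6.4.1.1) is a crude proportion in the FAS, obtained by "dividing the number of deaths by the number of FAS subjects, and a 2-sided exact 95% CI will be calculated". Losses count against the drug: "subjects who are lost to follow-up before day 42 will be counted as deaths".

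SAP 6.4.1.3, headed as sensitivity analysis, first repeats this without selection: "The primary efficacy endpoint will be analyzed as in Section 6.4.1.1 using the mFAS population". SAP 4.2 defines the mFAS as follows: "subset of the FAS subjects who have either probable or proven IA or IM diagnosis at baseline or up to 10 days after first dose". As an addition to that repeat, the section then states that "mFAS patients taking excluded concomitant medications used to treat IFDs will be eliminated for analysis of primary endpoint". It gives no time limit, no criterion for the reason for use, and no rationale. Protocol 7.4.1.2 plans only the mFAS repeat, so the deletion is introduced by the SAP.

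Three other places bear on the rule:

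- **What is excluded.** Protocol 5.1.2: "Use of other systemic antifungals is prohibited during study drug administration".
- **What is concomitant.** SAP 6.2.6: "Concomitant medications are defined as any medications that subjects took after the first dose of study medication and through 60 days post EOT". The same section also counts as concomitant any drug begun before study drug and continued alongside it.
- **Link to outcome.** In the adjudicated clinical response table (SAP 6.4.3.4), the progression category, which sits under failure, covers worsening or new findings "or if alternative systemic antifungal treatment is required".

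**The concern.** A sensitivity analysis should ask the same question as the primary analysis under a different assumption or data handling. This one changes who is counted, and it does so by something that happens during follow-up. Patients who take another antifungal leave both numerator and denominator, so what remains is mortality among patients who did not take one. That group cannot be identified at baseline.

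The trigger can be informative about outcome. The SAP itself places the need for an alternative antifungal under failure in the clinical response table. Timing matters as well: a patient must live long enough to receive another drug, so the earliest deaths are the least likely to be deleted.

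At stake is how the reader interprets agreement or disagreement. If the deleted rate is close to the primary rate, that does not show robustness. If it differs, the difference may reflect only who was removed. With about 30 subjects planned (SAP 3) and the mFAS a subset of them, a few deletions can move the rate a long way.

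**Working it through.** The plan gives no figure to reproduce: no mFAS size, no expected number taking other antifungals and no formal sample size calculation. The check therefore has two parts, one on the text and one illustrative.

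**1. When can the trigger occur?**

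- Wide reading (SAP 6.2.6): any time after the first dose to 60 days after end of treatment. With the maximum durations this is up to 84 + 60 = 144 days for IA and 180 + 60 = 240 days for IM.
- Narrow reading (Protocol 5.1.2, only while on study drug): up to day 84 for IA and day 180 for IM.

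Both readings extend beyond Day 42. A patient whose first use comes after Day 42 was alive on Day 42, so deleting that patient lowers the denominator only. It cannot reduce the Day 42 rate and, if there are any deaths, it raises it.

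**2. Which way does deletion move the rate?**

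Let the mFAS have N patients and D deaths, losses counted as deaths. Delete k patients, of whom d died.

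- Undeleted rate: D/N
- Deleted rate: (D − d)/(N − k)

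The two are equal when d/k = D/N. Deletion lowers the rate when the deleted patients died more often than the whole mFAS, and raises it when they died less often.

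*Assumed inputs:* N = 20, D = 6, k = 4. The death rate of 6/20 = 30.0% borrows the 12-week overall mortality in the prospective paediatric cohort described in Protocol 1.1, which is not a Day 42 figure. N and k are not in the documents. Intervals are exact (Clopper-Pearson) 95%.

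Undeleted: 6/20 = 30.0% (11.9 to 54.3). The break-even is d = 4 × 0.30 = 1.2 deaths.

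| Deaths among the 4 deleted | Deleted rate | 95% CI |
|---|---|---|
| 4 | 2/16 = 12.5% | 1.6 to 38.3 |
| 2 | 4/16 = 25.0% | 7.3 to 52.4 |
| 0 | 6/16 = 37.5% | 15.2 to 64.6 |

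*Range under other assumptions* (all deleted died, to none died):

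| mFAS, deaths | Undeleted | Deleted | Deleted rate, low to high |
|---|---|---|---|
| 20, 6 | 30.0% | 2 | 4/18 = 22.2% to 6/18 = 33.3% |
| 15, 4 | 26.7% | 4 | 0/11 = 0.0% to 4/11 = 36.4% |
| 25, 8 | 32.0% | 4 | 4/21 = 19.0% to 8/21 = 38.1% |

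Within each row the full mFAS data are fixed. Only the outcomes of the deleted patients change the result.

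**3. A composite that keeps everyone**

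Count death or start of another antifungal by Day 42: (D + k − d)/N. With the inputs of step 2, and all four starting by Day 42, this is 6/20 = 30.0% (11.9 to 54.3) if all four died and 10/20 = 50.0% (27.2 to 72.8) if none died.

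**The case against.** The case for leaving the text alone has real substance.

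- **The unselected analyses are already there.** The FAS primary analysis and the full mFAS repeat both stay, the deletion is an extra, and SAP 6.4 rules out formal inference. A reader can set the rates side by side. This stands, and it limits the severity.
- **Use is not the same as failure.** The clinical response table speaks of an alternative being required, which is an adjudicated judgement. The deletion rule speaks of taking an excluded drug, which is also a protocol deviation (PD4 in Protocol 8.3 and SAP 6.2.2). On the narrow reading it removes overlapping therapy, and a patient who stops study drug and then switches might not be deleted at all. Drugs carried over from before study drug also count as concomitant. This stands too: a reader might infer that every deleted patient is a treatment failure, and the documents do not say so.
- **It answers a per-protocol type of question.** Survival under overlapping therapy cannot be credited to study drug alone, so interest in patients without it is understandable. That justifies a descriptive subset. It does not make the subset a sensitivity analysis.
- **A composite is a different endpoint.** Correct. It cannot test the robustness of mortality, and it overlaps with the adjudicated clinical response at Day 42 (SAP 6.4.3). It belongs as supplementary information only.

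None of this supplies the missing time limit or removes the selection on a post-baseline event.

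**Conclusion.** The point holds in a limited form. The deletion in SAP 6.4.1.3 conditions a Day 42 mortality rate on a post-baseline event that can be related to outcome, and sets no time limit, so even a survivor of Day 42 can be removed for later use. It should not be called a sensitivity analysis of the primary endpoint.

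A reader might infer that the analysis is bound to make mortality look better. The documents do not support that. They give neither the frequency of such use nor the outcomes of those patients, and in the illustration an undeleted 30.0% can move to anything from 12.5% to 37.5%. Nor is the primary result compromised: it rests on all FAS subjects, and the undeleted mFAS rate is planned beside it.

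The selection and the missing time limit follow from the text. The sizes rest entirely on the assumed mFAS size, deaths and number deleted.

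**What to change.** In SAP 6.4.1.3:

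1. Name the undeleted mFAS rate, already planned, as the sensitivity analysis for Day 42 mortality.
2. Replace the deletion with a supplementary composite over the full mFAS denominator: death, or start of another systemic antifungal for the fungal infection, on or before Day 42. State that pre-study therapy carried over into the first days of study drug does not count as an event.
3. List each affected patient with the timing of use, its reason and the patient's outcome. SAP 6.2.6 already reports systemic antifungals separately, so the listing can build on that.
4. If the deletion analysis is kept, restrict the trigger to use on or before Day 42, say whether use after stopping study drug counts, and label the result a descriptive subset.

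The cost is SAP wording and one extra table. The composite will be at least as high as mortality alone and is a different endpoint, so the report must present it as such.

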7.4.2.2 Analysis of Additional Secondary Endpoints

Additional secondary efficacy endpoints include the overall, clinical, radiological and mycological response through day 42, day 84 and EOT. An Adjudication Committee (AC) will be utilized to confirm the diagnosis and overall, clinical, radiological and mycological response of IA or IM at each time point.

Crude success rates and 2-sided exact 95% CIs will be calculated and summarized for FAS and mFAS analysis sets.

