6.4.3 Analysis of Additional Secondary Efficacy Endpoints

Additional secondary efficacy endpoints will be overall, clinical, radiological and mycological response through day 42, day 84 and EOT. AC will assess all endpoints, Investigator's assessment include all endpoints except the overall response.

Each endpoint with the assessment criteria defined below will be summarized descriptively for FAS and mFAS populations through day 42, day 84 and EOT. Frequencies and 95% CI will be reported. All data will be represented in Listings by subject.

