6.4.3.7 AC-assessed Attributable Mortality

| Category | Outcome |
|------------------------------------|--|
| Directly Due to IFD | Death directly due to consequences of progressive IFD (clear evidence that mortality is due to progressive IFD) |
| Evidense Death Associated with IFD | Death associated with evidence of residual or ongoing IFD at time of death, but death may be due to IFD or progression of underlying disease |
| No Evidense Death Associated | Death associated with no evidence of residual or ongoing IFD) |
| Indeterminant | Indeterminant Cause |
| No Known Death | No Known Death |

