6.4.3.8 AC-assessed Overal Response

| Category | Outcome |
|-----------------|---|
| Success | 
 • Complete-Success • Partial-Success |
| Failure | 
 • Stable-Failure • Progression-Failure |
| Not Evaluable | 
 • Results Not Evaluable |

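### SAP 6.4.3 has no death rule for AC-assessed overall response; the only override is a Day 42 sensitivity analysis, so success rates at Day 84 and EOT can include patients who died.

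*SAP*

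**What the plan says.** **Endpoint.** SAP 5.2.2.2 lists "AC assessment of overall response at day 42, day 84 and EOT" among the additional secondary endpoints.

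**Main analysis.** SAP 6.4.3 states: "Each endpoint with the assessment criteria defined below will be summarized descriptively for FAS and mFAS populations through day 42, day 84 and EOT". Protocol 7.4.2.2 agrees: "Crude success rates and 2-sided exact 95% CIs will be calculated and summarized for FAS and mFAS analysis sets". Neither section mentions death.

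**Rating categories.** SAP 6.4.3.8 builds Success from two labels, of which "Complete-Success" is the first and a partial success the second. Stable and progressive disease are Failure, and there is a Not Evaluable row. Death is not listed. It is also absent from the AC clinical, mycological and radiological tables (SAP 6.4.3.4 to 6.4.3.6).

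**The one death rule.** It is filed under the primary (mortality) endpoint, and SAP 6.4.1.3 introduces it this way: "A secondary sensitivity analysis will apply a condition on the crude success rate of overall outcome of treatment evaluated by the AC on Day 42". Within that analysis, "Patients who die before or on Day 42 will be considered failures even if the DRC considers them successes". The trigger follows: "This sensitivity analysis will only be performed if any patient died by Day 42 is considered a success for treatment by the AC".

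**Where else death appears.** It appears in the all-cause mortality endpoints (SAP 6.4.1.1 and 6.4.2) and in the AC attributable-mortality table (SAP 6.4.3.7). One category there is "Death associated with no evidence of residual or ongoing IFD". Nothing links that table to overall response.

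**The concern.** The trigger in SAP 6.4.1.3 makes sense only if the AC can rate a patient who died by Day 42 as a success, and if that rating stays in the main table. The AC definitions leave room for this. Resolution of only some clinical findings is a clinical success (SAP 6.4.3.4). Mycological eradication can be presumed without post-baseline mycology if clinical findings have improved (SAP 6.4.3.5). A child whose infection improves and who then dies of the underlying disease could meet both.

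At Day 42 the SAP supplies a corrected rate when this happens. At Day 84, when more deaths will have accumulated, and at EOT it supplies none. A reader of those success rates would not know from the table whether every success was alive, and the SAP gives the programmer no rule. If the question came up only after the AC ratings were known, any choice could look data-driven.

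**Working it through.** The plan states no figure to reproduce: there is no sample size calculation and no assumed response rate. The check is therefore mainly textual, with simple arithmetic for size.

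**Step 1. Death rule by time point**

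| Time point | Main analysis of overall response (SAP 6.4.3, 6.4.3.8; Protocol 7.4.2.2) | Sensitivity analysis |
|---|---|---|
| Day 42 | none | death = failure, if triggered (SAP 6.4.1.3) |
| Day 84 | none | none |
| EOT | none | none |

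**Step 2. Shift per patient.** With all N subjects of the analysis set in the denominator, moving one patient from success to failure changes the rate by 100/N points.
- N = 30 (planned, Protocol 7.1): 100/30 = 3.3
- N = 25 (minimum evaluable, Protocol 2.2.1): 100/25 = 4.0
- N = 5 (minimum age cohort, Protocol 7.1): 100/5 = 20. With 25 evaluable subjects, at most one of the two cohorts can be this small.

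**Step 3. Illustration.** The success counts below are assumed, not taken from the documents. Intervals are exact (Clopper-Pearson) 95%.

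| N | AC successes | Of these, dead | Rate with death = failure | 95% CI |
|---|---|---|---|---|
| 30 | 18 | 0 | 18/30 = 60.0% | 40.6 to 77.3 |
| 30 | 18 | 1 | 17/30 = 56.7% | 37.4 to 74.5 |
| 30 | 18 | 2 | 16/30 = 53.3% | 34.3 to 71.7 |
| 30 | 18 | 3 | 15/30 = 50.0% | 31.3 to 68.7 |
| 25 | 15 | 0 | 15/25 = 60.0% | 38.7 to 78.9 |
| 25 | 15 | 1 | 14/25 = 56.0% | 34.9 to 75.6 |
| 25 | 15 | 3 | 12/25 = 48.0% | 27.8 to 68.7 |

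**Step 4. Will there be deaths?** Protocol 1.1 cites 30% mortality at 12 weeks in a paediatric cohort. If that applied here, 0.30 × 30 = 9 deaths would be expected by about Day 84 (0.30 × 25 = 7.5 at N = 25). If mortality were as low as an assumed 5%, the chance of at least one death in 30 would be 1 − 0.95^30 = 0.785. At 30% it exceeds 0.99. These figures bound the opportunity only. They do not say how many deaths the AC would rate as successes.

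**Step 5. What the EOT date captures.** The protocol's key terms define EOT as the date of the last dose. A patient cannot die before the last dose, so a rule covering deaths on or before EOT would catch only deaths on that same day. Any EOT rule therefore needs a later cut-off.

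**The case against.** The strongest case against is that response and mortality ask different questions. Mortality is the primary and key secondary endpoint and counts every death. A patient whose infection cleared and who died of leukaemia can reasonably be a responder and a death. The AC Charter (Protocol 10.2) is a separate document and may already settle the matter. The study is descriptive, overall response is an additional secondary endpoint, and all response data are listed by subject, so such a case could be found.

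Much of this stands. Whether death overrides response is a definitional choice, and the affected number may be zero. What remains is that the choice is not stated for the main analysis. A Charter rule making death a failure would leave the SAP 6.4.1.3 clause largely redundant, and the SAP should carry such a rule in any case.

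Four stronger readings are tempting and are not supported:
- **The conditional trigger hides something.** It does not. If no patient who died by Day 42 was rated a success, the corrected and uncorrected rates are identical. Otherwise the corrected rate and its exact interval are reported.
- **The response rate contradicts the mortality endpoint.** That is too strong, because SAP 6.4.3.7 separates death without residual infection from death due to it.
- **DRC is undefined.** This cannot be shown, because the part of the SAP abbreviation list where it would stand is not in the text available for review. What can be shown is that one paragraph uses both DRC and AC.
- **The primary endpoint is compromised.** It is not touched.

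**Conclusion.** The point holds as a gap in the response definition. Followed as written, the plan can report a patient who died as a success in the main overall-response analysis, with a correction available at Day 42 and none at Day 84 or EOT. The Step 2 shift per patient is certain arithmetic, given a fixed denominator. The total effect depends on AC ratings that nobody can predict, and even three such patients at N = 30 would move the estimate less than the width of its interval. It matters most in the planned age-cohort and infection-type summaries, where denominators are small.

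This should be corrected before the AC ratings are summarised. It does not threaten the study's main conclusions on mortality or safety.

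**What to change.** 1. In SAP 6.4.3 and 6.4.3.8, classify a subject who died on or before Day 42 or Day 84 as Failure for overall response at that time point in the main analysis.
2. For EOT, state a cut-off that includes deaths after the last dose, for example through the end of the EOT visit window (± 7 days in Protocol Tables 1 and 2).
3. Report the unmodified AC rating as the sensitivity analysis at Day 42, Day 84 and EOT.
4. Move the rule out of the mortality section (SAP 6.4.1.3) into 6.4.3, and use one committee name in place of the mixed DRC and AC.

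**Cost.** One SAP rule and a few extra table rows. No new data are needed: mortality status is already scheduled at Day 42 and at Day 84 or EOT (Day 180 or EOT for mucormycosis), and follow-up runs to 60 days after the last dose. The reported success rate may be slightly lower.
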